4.2 Study Activities Table

	Pre-Study	At Surgery	2 weeks post-surgery (+/- 5 days)	4 weeks post-surgery (+/- 5 days)	3-month Follow-up (+/- 5 days)
Informed consent	X				
Demographics	X				
Medical history					
• Surgical History	X				
Concurrent meds	X				
Physical exam	X				X
Vital signs	X				X
Wound Characteristics					
• Wound Class		X			
• Wound Depth					
• Wound Size					
Duration of Surgery	X	X			
Wound Assessment			X	X	X
Quality of life (SF-36)	X		X	X	X
CBC w/diff, platelets	X				
Comprehensive Metabolic Panel	X				
B-HCG (urine or serum)	X				
Adverse event evaluation		X	X	X	X

4.3 Experimental Methods

4.3.1 Patients will undergo standard of care surgery.

4.3.2 Study Group:

4.3.2.1 High risk clean contaminated wounds (class II) as defined with one of the following:

4.3.2.1.1 Obesity (BMI ≥ 30)

4.3.2.1.2 Subcutaneous depth ≥ 4 cm

4.3.2.1.3 ASA class ≥ 2

4.3.2.1.4 Duration of surgery (from surgery to closure) > 180 min

4.3.2.2 Contaminated wounds (class III)

4.3.2.3 Dirty/infected wounds (class IV)

4.3.3 Closure Technique:

Tertiary closure would involve the following:

- Fascial closure with PDS Plus
- Possible subcutaneous tissue approximation with Monocryl Plus at the surgeon's discretion
- Placement of a running subcuticular skin suture using an absorbable monofilament material such as PDS or Monocryl Plus without skin approximation
- Placement of a vacuum-assisted closure device over the incision at 125 mm Hg

- On Day # 4-7 (surgeon's discretion) at the bedside using sterile technique remove the VAC and approximate the skin edges using the previously placed subcuticular suture by pulling the suture ends and placing a hemoclip on the suture ends.
- Sutures would not require removal

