- Primary intention- all tissue including skin are closed with suture material.
- Secondary intention – in which wound is left open and close naturally.
- Tertiary intention – in which wound is left open for number of days and then closed if it found to be clean.

The **vacuum-assisted closure (VAC)** as noted above involves placement of a sterile sponge with negative continuous pressure proven to remove tissue fluid, increase blood supply and stimulate the wound thus decreasing time to healing. [6,7]

Also, ETHICON has developed suture impregnated with TRICLOSAN as an antimicrobial proven to reduce some surgically related infections.

- CDC Guidelines for the Prevention of Surgical Site Infections 2017
 - Consider the use of triclosan-coated sutures for the prevention of SSI. [8]
- WHO Global Guidelines for The Prevention of Surgical Site Infection
 - The panel suggests the use of triclosan coated sutures for the purpose of reducing the risk of SSI, independent of type of surgery. [9]
- American College of Surgeons Surgical Infection Society
- The use of triclosan coated suture is recommended for wound closure in clean and clean contaminated cases when available. [10]

Abstract

Introduction

Surgical site infections (SSI) following gynecological abdominal surgeries are associated with prolonged wound healing, additional procedural costs and a lower quality of life. The purpose of this study is to describe an alternative wound closure

technique (tertiary closure) aimed at improving wound morbidity for high-risk patients compared to healing by secondary intention.

Methods

Patients undergoing surgery at high-risk (class III or III wound) for developing SSI were enrolled. Tertiary closure was performed by: 1) running a subcuticular absorbable monofilament suture with looping of the suture every 8-10 cm through the skin secured with hemoclips and by 2) placing a vacuum assisted closure (VAC) over the incision. On post-operative day four (POD #4), the incision was re-approximated at the bedside by removing the VAC and applying traction on the suture using hemoclips.

Results

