2.0 Objectives

2.1 Primary Objective

2.1.1 To compare the percentage of patients whose wound remained closed on postoperative day #30 after tertiary closure compared to historical controls who underwent secondary wound closure. We are primarily looking at time to wound closure. We will be able to abstract this information from the postoperative clinic visit notes from patients in the "historical control" cohort. We will identify 20 patients with characteristics described in the inclusion criteria of this study who underwent laparotomy with secondary wound closure during the calendar year 2018.

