4.3.4 Patient Follow-up and Data Collection

- 4.3.4.1 After surgery, the removal of the VAC and closing of the superficial aspects of the wound will be performed based on the physician's discretion.
- 4.3.4.2 Patients will be monitored per standard of care procedures to assess infection, wound dehiscence, and wound complications.
- 4.3.4.3 Wound closure will be noted.
- 4.3.4.4 When the patient is discharged the time will be noted.

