Appendix F - Wound Form

Visit: 2 weeks 4 weeks 3 months

Date of encounter (mm/dd/yyyy): ____/____/_____

1. Infection: Yes No

If yes, date infection occurred: (mm/dd/yyyy): ____/____/_____

2. Did Wound Dehiscence occur? Yes No

If yes, date: (mm/dd/yyyy): ____/____/_____

Physician's assessment of why dehiscence occurred:

3. Percentage of wound healing: _____%

4. Day of hospital discharge (mm/dd/yyyy): ____/____/_____

5. Post-surgery date wound is closed

(mm/dd/yyyy): ____/____/_____

6. Is the wound closed on POD # 30? Yes No

7. Wound Complications (free text):

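### The condition and timing for drawing the wound closed are not stated consistently, and the undefined closure date on the Wound Form can mix a procedure date with a healing outcome

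*Combined protocol and SAP*

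**What the plan says.** **Whether and when the wound is drawn closed**

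- Section 1.0, list of three wound techniques: tertiary intention is the one "in which wound is left open for number of days and then closed if it found to be clean".
- Section 4.3.3, for a day from Day 4 to Day 7 that the surgeon chooses: "at the bedside using sterile technique remove the VAC and approximate the skin edges". Discretion attaches to the day. No wound condition is given.
- Section 4.3.4.1: "the removal of the VAC and closing of the superficial aspects of the wound will be performed based on the physician's discretion". No window is given.
- Sections 3.1.1 and 4.3.2.3: dirty or infected (class IV) wounds are eligible.

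**What is recorded**

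- Appendix F (Wound Form) is completed at 2 weeks, 4 weeks and 3 months. Item 5 asks for "Post-surgery date wound is closed". The same form records dehiscence with its date (item 2), percentage of healing (item 3) and whether the wound is closed on day 30 (item 6).
- Neither Appendix E nor Appendix F has a field for VAC removal or skin approximation. Section 4.3.4.3 says only that closure is noted.

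**What is to be compared**

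- Section 2.1.1: "We are primarily looking at time to wound closure". The control information is to be abstracted from postoperative clinic notes.
- Section 5.1.1 defines the primary outcome as closed status on day 30. Sections 6.1 and 6.3 describe the analysis as closure within 30 days.

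**The concern.** The bedside approximation is what distinguishes the studied technique from healing by secondary intention. A reader cannot tell from the documents whether a wound that is not clean at that step is to be approximated, or how a patient whose wound is never approximated is counted. With class IV wounds eligible, that situation is foreseeable, and it bears on patient safety as well as on what the intervention is.

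The recording problem follows from the same gap. A closure date that may mean skin edges drawn together, or may mean wound healed, does not measure one thing. If it is used for time to closure, a procedure scheduled by the surgeon in one group is set against a biological outcome in the other. If it is used to decide closure within 30 days, it can hide re-opening. Section 5.2.4 says that whether these wounds stay closed is unknown and gives that as the reason for the 30-day endpoint.

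**Working it through.** **1. The statements on approximation, side by side**

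| Place | Condition on the wound | Day |
|---|---|---|
| 1.0, definition | must be found clean | an unspecified number of days |
| 4.3.3 | none stated | Day 4 to 7, surgeon's discretion |
| 4.3.4.1 | none stated | physician's discretion, no window |

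Take a class IV wound that is not clean on Day 5. The definition does not close it, 4.3.3 read literally approximates it by Day 7, and 4.3.4.1 leaves it to judgement. No section says how the patient is counted if approximation does not happen.

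**2. What the closure date can mean in each group**

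In a tertiary patient, item 5 can be filled with the approximation date (Day 4 to 7 under 4.3.3) or with a later healing date, because closed is not defined. In a control, section 1.0 says the wound is left to close naturally, so the date abstracted from the notes can only be a healing date. If the approximation date is entered, time to closure in the tertiary group is 4 to 7 days whatever happens to the wound afterwards. The shorter time expected in 5.2.4 is then partly built in.

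**3. The re-opened wound**

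Take a wound approximated on Day 5, re-opened, and open on day 30.

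- By item 5 read as the approximation date, 5 ≤ 30, so it is closed within 30 days (wording of 6.1 and 6.3).
- By item 6, it is not closed on day 30 (5.1.1).

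With 20 tertiary patients, each such case changes the primary proportion by 1/20 = 5 percentage points.

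**4. The plan's own power figure**

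Inputs from 6.1: 20 tertiary patients, 100 controls, two-sided 0.05, closure near 100% against near 0%, stated power above 90%. No exact rates are given, so a range is assumed. The formula is power = Φ[(d − 1.96·se0)/se1], where d is the difference in proportions, se0 the pooled and se1 the unpooled standard error.

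For 80% against 20%, with 100 controls: pooled proportion (16 + 20)/120 = 0.30; se0 = √(0.30 × 0.70 × (1/20 + 1/100)) = 0.1122; se1 = √(0.16/20 + 0.16/100) = 0.0980; (0.60 − 0.2200)/0.0980 = 3.88, so power is 99.99%.

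| Assumed rates | 100 controls (6.1) | 20 controls (2.1.1) |
|---|---|---|
| 95% v 5% | about 100% | about 100% |
| 90% v 10% | about 100% | about 100% |
| 80% v 20% | 99.99% (Fisher exact 99.96%) | 98.9% (Fisher exact 96.1%) |
| 70% v 5% | about 100% | 99.9% |

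The stated power reproduces. The last row lets 30% of tertiary wounds be not closed, and power still holds. The two control numbers are a separate matter; both are shown so that this result does not depend on which is right.

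**5. Time at risk of re-opening by day 30**

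- Approximated on Day 4: 30 − 4 = 26 days. On Day 7: 30 − 7 = 23 days. The spread is 3 days, and 3/26 = 11.5%.
- If status is read at the 4-week visit (28 ± 5, so day 23 to 33), the range is 23 − 7 = 16 to 33 − 4 = 29 days. The visit window adds more spread than the choice of day.
- If the re-opening risk over 26 days were 10%, 20% or 40% (assumed) at a constant hazard, the risk over 23 days is 1 − (1 − r)^(23/26) = 8.9%, 17.9% or 36.4%. The reductions are 1.1, 2.1 and 3.6 points. With risk concentrated early (hazard half-life of 7 days, assumed), they are 0.3, 0.5 and 0.9 points.

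**The case against.** The case on the other side has real force.

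- **The sections can be read together.** 4.3.3 and 4.3.4.1 both grant discretion, and the second can be taken as restating discretion inside the first's window. The clean-wound condition sits in a background definition, not in a study procedure. This stands in part: these are not opposite orders. But an operative section that omits the condition by which the technique is defined, in a trial that enrols infected wounds, still leaves the reader without one rule.
- **Day 4 in the earlier case series.** A reader might infer a third competing rule from "On post-operative day four (POD #4), the incision was re-approximated at the bedside". The documents do not support that. It describes earlier patients, and Day 4 lies inside Day 4 to 7.
- **The form is richer than item 5.** It is completed at each visit, dates dehiscence, and has its own day-30 item. This stands. A reader might infer that item 5 is always the procedure date, but the form does not say so. The defect is that the date is undefined, not that re-opening goes unrecorded.
- **Time to closure is not analysed.** Section 6 contains no such analysis and the defined primary outcome is binary. This stands, so no planned test is biased through that route. The sentence in 2.1.1 still presents time to closure as the main interest, and it invites a comparison that the data cannot fairly support.
- **Length of stay.** A reader might infer that the chosen day sets length of stay, since the step is at the bedside and the case series had a median stay of 4 days. No section ties discharge to approximation. Length of stay may reflect that day; the documents do not show that it does.

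**Conclusion.** The concern holds in a limited form, and the plan should be changed. Three things are established from the text:

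1. The condition and timing for approximation are not stated consistently and must be reconciled.
2. Item 5 is undefined and can carry different meanings in the two groups, so time to closure is not a fair outcome comparison.
3. The wording of 6.1 and 6.3 would allow a wound that was approximated and then re-opened to be counted as closed, against 5.1.1, at 5 percentage points per patient.

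How many patients this would affect cannot be estimated from the documents. It depends on how item 5 is completed and on whether the analysis uses item 5 or item 6.

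A reader might go further and infer that the choice of day materially distorts the day-30 endpoint or undermines the power. Neither is supported. Within Day 4 to 7 the time at risk differs by at most 3 days, item 6 does not use the closure date, and power stays above 90% under every set of rates tabulated above.

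**What to change.** - Reconcile the definition in 1.0 with 4.3.3 and 4.3.4.1, so that the protocol carries one statement of the condition and timing for approximation. The clinical rule is for the investigators to set. State also how a patient whose wound is not approximated is counted.
- Replace Appendix F item 5 with separate fields: approximated yes/no and date, and date of final closure after any re-opening. Define closed for the second field, and apply that definition when abstracting the controls.
- In 2.1.1, delete the sentence that makes time to closure the main interest, or label it a procedure time in the tertiary group.
- In 6.1 and 6.3, replace closure within 30 days by closed status on day 30, taken from item 6, to match 5.1.1.
- When length of stay is reported, show the day of approximation beside it.

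The cost is protocol wording and a few form fields for a bedside step that already takes place. No extra visits or patients are needed.

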4.3.4 Patient Follow-up and Data Collection

- 4.3.4.1 After surgery, the removal of the VAC and closing of the superficial aspects of the wound will be performed based on the physician's discretion.
- 4.3.4.2 Patients will be monitored per standard of care procedures to assess infection, wound dehiscence, and wound complications.
- 4.3.4.3 Wound closure will be noted.
- 4.3.4.4 When the patient is discharged the time will be noted.

5.0 Outcome Measures

5.1 Primary Outcomes

- 5.1.1 The percentage of patients whose wound is closed on postoperative day # 30 after tertiary wound closure compared to historical controls who underwent secondary wound closure.

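### The primary endpoint, wound closed at day 30, has no criterion common to both groups, and sections 6.1 and 6.3 time it differently from the objective and the outcome

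*Combined protocol and SAP*

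**What the plan says.** The primary objective (2.1.1) is "To compare the percentage of patients whose wound remained closed on postoperative day #30 after tertiary closure", against historical controls with secondary closure. The same paragraph adds "We are primarily looking at time to wound closure". The primary outcome (5.1.1) is "The percentage of patients whose wound is closed on postoperative day # 30 after tertiary wound closure", again against those controls. Sections 6.1 and 6.3 then power and test the proportion closed within 30 days.

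The groups reach closure by different routes. For tertiary closure, section 4.3.3 has the surgeon remove the VAC on day 4-7 and "approximate the skin edges using the previously placed subcuticular suture by pulling the suture ends". Section 1.0 describes secondary intention as healing "in which wound is left open and close naturally".

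The recording also differs. Section 4.3.4.3 says only that closure will be noted. Appendix F has a Yes/No item, "Is the wound closed on POD # 30", and a separate item, "Percentage of wound healing", with no link between them. For controls, section 2.1.1 takes the information from postoperative clinic notes of patients operated on in 2018.

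Section 5.2.4 explains why day 30 was chosen: it is not known whether tertiary wounds stay closed.

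**The concern.** The word carrying the primary endpoint has no criterion. The contrast with infection is plain, since section 6.2.1 lists the signs that make up a wound infection. Without a criterion, a sutured incision with a short gap or some drainage can be ticked as closed, while a control wound with a similar small defect can be read from a note as still open. Nothing in the plan prevents this. Lenient coding of tertiary wounds would favour the new technique.

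The timing wording adds a second problem. Being closed on day 30 requires the wound to have held. Having closed within 30 days does not: a wound sutured on day 4-7 meets it on that day, whatever follows. The durability question in 5.2.4 is answered only under the first reading.

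What is at stake is the meaning of a positive result. A contrast of about 100% against about 0% is largely what one expects when one group is sutured and the other is left open. It does not by itself show that tertiary wounds are intact at day 30.

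**Working it through.** **Inputs.** Tertiary n = 20 (6.1). Controls n = 100 (6.1) or 20 (2.1.1); the two sections disagree, which is a separate matter, so both are shown. Two-sided alpha 0.05, stated power above 90%, expected rates close to 100% and close to 0% (6.1). Chi-squared test (6.3). The plan gives no exact rates, so those below are assumptions.

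**1. The stated power reproduces.** Take 80% v 20%, which is less extreme than the plan expects. The pooled normal approximation is power = Φ[(|p1 − p2| − 1.96·SE0)/SE1], where SE0 = √[p̄(1 − p̄)(1/n1 + 1/n2)] and SE1 = √[p1(1 − p1)/n1 + p2(1 − p2)/n2].

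- 20 v 100: p̄ = (16 + 20)/120 = 0.30, SE0 = √(0.21 × 0.06) = 0.1122, SE1 = √(0.0080 + 0.0016) = 0.0980. Then (0.60 − 0.2200)/0.0980 = 3.88, and power exceeds 99.9%.
- 20 v 20: p̄ = 0.50, SE0 = 0.1581, SE1 = 0.1265. Then (0.60 − 0.3099)/0.1265 = 2.29, and power = 98.9% (96-98% by exact enumeration).

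At 90/10, 95/5 and 99/1, power is about 100% for either number of controls. The power claim is not in dispute.

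**2. How little durability the test requires.** The table gives the smallest number of tertiary wounds closed, out of 20, that makes p ≤ 0.05.

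| Controls closed | Chi-squared, uncorrected | Continuity-corrected | Fisher |
|---|---|---|---|
| 0 of 100 | 1 | 2 | 2 |
| 5 of 100 | 4 | 5 | 4 |
| 10 of 100 | 6 | 6 | 6 |
| 0 of 20 | 4 | 6 | 5 |

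For the first row:

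- 1 of 20 v 0 of 100, uncorrected: χ² = 120 × (1 × 100 − 19 × 0)² / (20 × 100 × 1 × 119) = 1,200,000/238,000 = 5.04, p = 0.025. The smallest expected count is 20 × 1/120 = 0.17, so the approximation is poor here.
- 2 of 20 v 0 of 100, Fisher: C(20,2)/C(120,2) = 190/7,140 = 0.027.

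So 18 of 20 tertiary wounds could be open on day 30 and Fisher's test would still be significant. With a true tertiary rate of 40% and a control rate of 1-5% (assumed), power for 20 v 100 remains 97-99.9%.

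**3. What coding does to the tertiary proportion.** One patient is 1/20 = 5 percentage points. The exact (Clopper-Pearson) lower 95% limit is the 2.5th percentile of Beta(x, 21 − x). For 20 of 20 this is 0.025^(1/20) = 0.832.

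| Closed | Proportion | Lower 95% limit |
|---|---|---|
| 20 of 20 | 100% | 83.2% |
| 19 of 20 | 95% | 75.1% |
| 18 of 20 | 90% | 68.3% |
| 17 of 20 | 85% | 62.1% |

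The lower rows illustrate one, two or three patients recoded as not closed. The documents give no rate for partly separated wounds.

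**4. The two timing readings.** Take a tertiary wound sutured on day 5 and open from day 20 to day 35. Under 2.1.1 and 5.1.1 it is a failure. Under 6.1 and 6.3, read literally, it is a success. Appendix F item 5 would supply a closure date of day 5. Only item 6 records the day-30 state.

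**The case against.** The strongest reply is that the endpoint does require durability. The objective says remained closed, section 5.2.4 gives durability as the reason for day 30, and approximation happens on day 4-7, so the wound must hold for about three more weeks. Section 10.1.1 says a deeper infection typically leads to re-opening, and a wound still open on day 30 would fail. This stands. A reader might infer that the procedure alone meets the endpoint, but 2.1.1, 5.1.1 and 5.2.4 do not support that. It follows only from the literal wording of 6.1 and 6.3.

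Three further inferences also go too far.

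- **Two definitions of closed.** The protocol does not define the word one way for each group. It defines it for neither, and the difference is inferred from the technique descriptions in 1.0 and 4.3.3. An undefined term permits unequal coding but does not prescribe it.
- **Coding by the treating surgeon.** No assessor is named for closure. Only the reason for dehiscence asks for a physician's assessment.
- **Recoding would overturn the result.** It would not. At 17 of 20 against a control rate near 0%, the planned test is still clearly positive. The pilot series in 1.0, six patients with no wound complications at sixty days, gives no support for a 15% rate, though it is too small to exclude one.

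It is also fair that infection, length of stay, return within 30 days and quality of life are assessed separately, so patient benefit does not rest on this endpoint alone. None of this supplies the missing criterion or reconciles the two timings.

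**Conclusion.** The concern holds in a limited form. The endpoint has no stated criterion, closure is produced by suture in one group and by natural healing in the other, and its status is recorded prospectively in one and read from old notes in the other. The groups can therefore be scored by different standards. Separately, sections 6.1 and 6.3 use a timing that does not match 2.1.1 and 5.1.1 and that, taken literally, ignores re-opening.

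The between-group test is unlikely to change, because it is close to decided by the expected contrast: 2 of 20 against 0 of 100 is enough by Fisher. The effect falls on the tertiary group's own day-30 proportion, at 5 points per patient. Recoding one to three patients (assumed) would take the exact lower limit from 83.2% to between 75.1% and 62.1%. The conclusion about the test rests on the plan's own expectation that controls are near 0%. The change should be made before outcomes are coded.

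**What to change.** - **Define the state.** In 5.1.1 and Appendix F item 6, define closed on postoperative day 30 by one observable wound state for both groups, for example skin continuous along the whole incision with no open area, drainage or packing. A wound that has re-opened and is open on day 30 counts as not closed.
- **Align the timing.** In 6.1 and 6.3, replace closure within 30 days with closure on postoperative day 30.
- **Apply it to the controls.** Use the same criterion in chart abstraction, with a stated rule for notes that cannot be classified and a sensitivity analysis counting them each way. Do not require 100% on the healing-percentage item for controls, since nothing in the plan says they have that value.
- **Report separately.** Give initial skin-edge approximation as a procedural result, and the tertiary day-30 proportion with an exact 95% confidence interval.

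**Cost.** Wording in four places and an abstraction rule, with no new procedure. The existing 4-week visit can supply the assessment, but its window of ±5 days runs from day 23 to day 33, so the form should say how an earlier visit is used. The tertiary percentage may be slightly lower, and some control notes may be unclassifiable. Power on the new definition cannot be stated, because the documents give no rate for it. For illustration, with assumed control rates of 10-50%, 20 v 100 keeps more than 90% power at a difference of 40 points (93-97% by normal approximation, 91-97% by Fisher). With 20 v 20, 40 points gives only 73-81% and 60-74%.
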